Bandage Contact Lens Application for the Management of Corneal Abrasion in the Emergency Department

NCT04159714

January 24, 2019

IRB Minimal Risk Protocol Template

General Study Information

Principal Investigator: [name].

Study Title: Bandage Contact Lens Application for the Management of Corneal Abrasion in the Emergency Department

Protocol version number and date: V2. 1/24/2019

Research Question and Aims

Hypothesis: Will the use of a bandage result in alleviation of symptoms from corneal abrasions.

Aims, purpose, or objectives: This study is designed to answer the following questions:

- I. Does the use of a bandage contact lens decrease pain and discomfort associated with corneal abrasion?
- II. Is the addition of bandage contact lens more helpful in alleviating the pain associated with corneal abrasion compared with current practice/usual care (topical antibiotic ointment, oral analgesia, etc.)?
- III. Is the use of a bandage contact lens a safe and practical intervention for emergency physicians to administer and for patients to use?

Background (*Include relevant experience, gaps in current knowledge, preliminary data, etc.*):

Corneal abrasion is a traumatic erosion of the corneal surface, often resulting from accidental contact by fingernails, hairbrushes, airborne particles, branches and other suspended objects, as well as from poor contact lens technique or over-wear. Most corneal abrasions heal spontaneously within 48 hours, but significant pain at the time of injury prompts many patients to visit the Emergency Department for evaluation and symptomatic management. Management usually includes topical antibiotic ointment and analgesia; however, there is widespread variation in treatment, consultation with ophthalmology and follow-up patterns. To my knowledge, the use of bandage contact lenses has not been prospectively studied in the Emergency Department. Although the use of bandage contact lenses is described in Roberts and Hedges Clinical Procedures in Emergency Medicine and Acute Care, Seventh edition, this practice has not gained widespread acceptance in most Emergency Departments. Because the pain associated with corneal abrasions is often significant and frequently results in opioid prescribing, bandage contact lens use offers the potential for avoidance of these medications as well.

Study Design and Methods

Methods: *Describe, in detail, the research activities that will be conducted under this protocol:*

A randomized trial of a bandage contact lens or usual care will occur in patients presenting to the Emergency Department. Patients diagnosed with superficial corneal abrasion in the Emergency Department will be asked to participate in the study. After voluntary, informed consent has been obtained, those patients wishing to

participate will be randomized (www.randomization.com) to the bandage contact lens (BCL) group or usual care (UC). Using a validated pain scale, subjects will be asked to rate their level of pain before treatment and immediately after treatment in the ED. BCL subjects will have a BCL soaked in antibiotic solution placed in the affected eye. UC subjects will have usual care provided in the ED per the ED consultant.

- Patients in both groups will be contacted **via telephone** between 12-24 hours after ED treatment to assess their pain scores. Additional questions pertaining to comfort, complications, etc. may also be queried at that time. Patients will be re-contacted **via telephone** between 36-48 hours after ED treatment to assess their pain scores. Additional questions pertaining to comfort, complications, etc. may also be queried at that time.

A follow-up appointment with Ophthalmology will occur at 1 day, 3 days, and/or 5 days post-discharge, depending on specific patient factors, patient needs, clinic availability, day of the week, etc. **This follow-up appointment is standard of care; any patient presenting to the ED with a corneal abrasion will be scheduled for a follow-up visit with Ophthalmology.** The contact lens will be removed when the examining follow-up provider has deemed that the abrasion has healed. This will be communicated to the patient in the ED following enrollment, in the patient follow-up instructions document (attached in participant contact materials), and in the letter to the follow-up provider (attached in participant contact materials). All patients will be given follow-up instructions regarding when to return to the ED, ophthalmology clinic, etc. for BCL removal and recheck prior to ED discharge. The use of oral analgesia, including opioids, NSAIDs and/or acetaminophen will also be recorded and quantified across the two groups.

Data will be obtained from the follow-up ophthalmology visit regarding safety, adverse events and any complication of the lens wear.

Resources: *Describe the available resources to conduct the research (personnel, time, facilities, mentor commitment, etc.):* Recruitment will take place in the SMH Emergency Department by the EM consultant and/or the ED research coordinators. ED patients presenting to the ED with acute eye pain will be screened to determine if they meet eligibility requirements for this study.

(1a) This is a multisite study involving Mayo Clinic and non Mayo Clinic sites. *When checked, describe in detail the research procedures or activities that will be conducted by Mayo Clinic study staff.*

(1b) Mayo Clinic study staff will be engaged in research activity at a non Mayo Clinic site. *When checked, provide a detailed description of the activity that will be conducted by Mayo Clinic study staff.*

Subject Information

Target accrual is the proposed total number of subjects to be included in this study at Mayo Clinic. A “Subject” may include medical records, images, or specimens generated at Mayo Clinic and/or received from external sources.

Target accrual: 200

Subject population (children, adults, groups): Patients >18 years of age presenting to the Emergency Department with superficial corneal abrasion due to trauma.

Inclusion Criteria: Diagnosis of Superficial Corneal Abrasion

Exclusion Criteria:

- Incarceration
- Pregnancy
- Inability to Provide Informed Consent
- Infectious keratitis
- Retained foreign bodies in the eye
- Active infection involving the orbit or periorbital region
- Patients who are not able to or who are deemed unlikely to follow-up with ophthalmology
- A history or recent contact lens wear
- A lack of trauma or an unclear history of trauma as the inciting cause of the abrasion
- Allergy to the antimicrobial solution (POLYTRIM)
- Women who are currently breastfeeding
- Chronic eye drop use
- A history of eye surgery other than cataract surgery (greater than 6 months prior to abrasion)
- Diabetes (Patients with even mild diabetic neuropathy can have decreased pain sensation and also delayed corneal epithelial healing)
- Any eye condition that may be deemed to interfere with the conduct of the protocol or outcome measurement.

Research Activity

Check all that apply and complete the appropriate sections as instructed.

1. **Drug & Device:** Drugs for which an investigational new drug application is not required. Device for which (i) an investigational device exemption application is not required; or the medical device is cleared/approved for marketing and being used in accordance with its cleared/approved labeling. (Specify in the Methods section)
2. **Blood:** Collection of blood samples by finger stick, heel stick, ear stick, or venipuncture.

3. **Biological specimens other than blood:** Prospective collection of human biological specimens by noninvasive means that may include: urine, sweat, saliva, buccal scraping, oral/anal/vaginal swab, sputum, hair and nail clippings, etc.
4. **Tests & Procedures:** Collection of data through noninvasive tests and procedures routinely employed in clinical practice that may include: MRI, surface EEG, echo, ultrasound, moderate exercise, muscular strength & flexibility testing, biometrics, cognition testing, eye exam, etc. (Specify in the Methods section)
5. **Data** (medical record, images, or specimens): Research involving use of existing and/or prospectively collected data.
6. **Digital Record:** Collection of electronic data from voice, video, digital, or image recording. (Specify in the Methods section)
7. **Survey, Interview, Focus Group:** Research on individual or group characteristics or behavior, survey, interview, oral history, focus group, program evaluation, etc. (Specify in the Methods section)

NIH has issued a *Certificate of Confidentiality* (COC). *When checked, provide the institution and investigator named on the COC and explain why one was requested.* _____

Biospecimens – Categories 2 and 3

(2) Collection of blood samples. When multiple groups are involved copy and paste the appropriate section below for example repeat section b when drawing blood from children and adults with cancer.

- a. **From healthy, non-pregnant, adult subjects who weigh at least 110 pounds.** For a minimal risk application, the amount of blood drawn from these subjects may not exceed 550ml in an 8 week period and collection may not occur more frequently than 2 times per week.

Volume per blood draw: _____ ml

Frequency of blood draw (e.g. single draw, time(s) per week, per year, etc.) _____

- b. **From other adults and children considering age, weight, and health of subject.** For a minimal risk application, the amount of blood drawn from these subjects may not exceed the lesser of 50 ml or 3 ml per kg in an 8 week period, and collection may not occur more frequently than 2 times per week.

Volume per blood draw: _____ ml

Frequency of blood draw (e.g. single draw, time(s) per week, per year, etc.) _____

(3) Prospective collection of biological specimens other than blood: _____

Review of medical records, images, specimens – Category 5

For review of existing data: provide a date range or an end date for when the data was generated. The end date can be the date this application was submitted to the IRB. Example: *01/01/1999 to 12/31/2015* or all records through *mm/dd/yyyy*.

Date Range:

Check all that apply (data includes medical records, images, specimens).

(5a) Only data that exists before the IRB submission date will be collected.

(5b) The study involves data that exist at the time of IRB submission **and** data that will be generated after IRB submission. Include this activity in the Methods section.

Examples

- The study plans to conduct a retrospective chart review and ask subjects to complete a questionnaire.
- The study plans to include subjects previously diagnosed with a specific disease and add newly diagnosed subjects in the future.

(5c) The study will use data that have been collected under another IRB protocol. Include in the Methods section and enter the IRB number from which the research material will be obtained. *When appropriate, note when subjects have provided consent for future use of their data and/or specimens as described in this protocol.*

Enter one IRB number per line, add more lines as needed

Data Specimens Data & Specimens _____

Data Specimens Data & Specimens _____

Data Specimens Data & Specimens _____

(5d) This study will obtain data generated from other sources. Examples may include receiving data from participating sites or an external collaborator, accessing an external database or registry, etc. Explain the source and how the data will be used in the Methods section.

(6) Video audio recording: *Describe the plan to maintain subject privacy and data confidentiality, transcription, store or destroy, etc.*

HIPAA Identifiers and Protected Health Information (PHI)

Protected health information is medical data that can be linked to the subject directly or through a combination of indirect identifiers.

Recording identifiers (including a code) during the conduct of the study allows you to return to the medical record or data source to delete duplicate subjects, check a missing or questionable entry, add new data points, etc. De-identified data is medical information that has been stripped of all HIPAA identifiers so that it cannot be linked back to the subject. De-identified data is **rarely** used in the conduct of a research study involving a chart review.

Review the list of subject identifiers below and, if applicable, check the box next to each HIPAA identifier being recorded at the time of data collection or abstraction. Identifiers apply to any subject enrolled in the study including Mayo Clinic staff, patients and their relatives and household members.

Internal refers to the subject's identifier that will be recorded at Mayo Clinic by the study staff.

External refers to the subject's identifier that will be shared outside of Mayo Clinic.

Check all that apply:	INTERNAL	EXTERNAL
Name	X	
Mayo Clinic medical record or patient registration number, lab accession, specimen or radiologic image number	X	
Subject ID, subject code or any other person-specific unique identifying number, characteristic or code that can link the subject to their medical data	X	
Dates: All elements of dates [month, day, and year] directly related to an individual, their birth date, date of death, date of diagnosis, etc.	X	
Note: Recording a year only is not a unique identifier.		
Social Security number		
Medical device identifiers and serial numbers		
Biometric identifiers, including finger and voice prints, full face photographic images and any comparable images		
Web Universal Resource Locators (URLs), Internet Protocol (IP) address numbers, email address		
Street address, city, county, precinct, zip code, and their equivalent geocodes		
Phone or fax numbers		
Account, member, certificate or professional license numbers, health beneficiary numbers		
Vehicle identifiers and serial numbers, including license plate numbers		
Check 'None' when none of the identifiers listed above will be recorded, maintained, or shared during the conduct of this study. (exempt category 4)	 None	 None

Data Analysis

Data Analysis Plan: Comparison of pain scores. Will also evaluate and determine if there are any advantages/disadvantages to application of BCL versus usual care.

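### Complication questions are optional at both telephone calls, so early problems can be recorded unevenly; the only required safety data come from an ophthalmology visit that may first fall on day 3 or day 5

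*Protocol*

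**What the plan says.** All of the data collection on this point is in the Protocol, Study Design and Methods.

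- **Calls.** "Patients in both groups will be contacted" by telephone 12 to 24 hours after treatment in the emergency department (ED), and again "between 36-48 hours after ED treatment to assess their pain scores". The pain score is the required content of each call. After each call the same sentence follows: "Additional questions pertaining to comfort, complications, etc. may also be queried at that time".
- **Required safety data.** "Data will be obtained from the follow-up ophthalmology visit regarding safety, adverse events and any complication of the lens wear". The appointment is standard of care for corneal abrasion, so it is due in both arms. It takes place at "1 day, 3 days, and/or 5 days post-discharge, depending on specific patient factors, patient needs, clinic availability, day of the week".
- **Analgesics.** Here the wording is mandatory: "The use of oral analgesia, including opioids, NSAIDs and/or acetaminophen will also be recorded and quantified across the two groups".
- **Return.** Before discharge, all patients receive "follow-up instructions regarding when to return to the ED, ophthalmology clinic, etc. for BCL removal and recheck".

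Two other sections depend on these data. Aim III, under Research Question and Aims, asks: "Is the use of a bandage contact lens a safe and practical intervention for emergency physicians to administer and for patients to use". The Data Analysis Plan intends to weigh the benefits and drawbacks of the lens against usual care.

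**The concern.** The two calls are the only post-discharge contacts with set time windows that apply to every patient in both arms. They are the natural place to collect early safety information in a comparable way. As written, a caller complies with the protocol whether or not complications are raised, and nothing fixes what is asked or how.

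This matters for two reasons. First, a call record with no complication is ambiguous: the patient may have had none, or may not have been asked. Second, a lens in the eye and usual care are plainly distinguishable, so a caller who knows the treatment is free to question patients differently. The safety part of the lens-versus-usual-care comparison would then rest partly on uneven information. No later analysis can recover an answer to a question that was not asked, so this cannot be left to an analysis plan.

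**Working it through.** The protocol states no figure to reproduce. The check is a comparison of what is required with what is optional, plus a conversion of days to hours. Inputs are the call windows and visit days in Study Design and Methods. Assumptions: a day counts as 24 hours, and ED treatment and discharge are taken as the same moment.

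**Step 1. Required against optional, by contact.**

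| Contact | Timing | Required | Optional |
|---|---|---|---|
| Call 1 | 12-24 h | Pain score | Comfort and complication questions |
| Call 2 | 36-48 h | Pain score | Comfort and complication questions |
| Ophthalmology visit | Day 1, 3 and/or 5 | Safety, adverse events, lens complications | None stated |

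The protocol uses mandatory wording where it wants an item collected, as it does for oral analgesics. No other section makes the complication questions mandatory.

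**Step 2. Visit days in hours.** 1 × 24 = 24 h; 3 × 24 = 72 h; 5 × 24 = 120 h.

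**Step 3. Where a first visit falls relative to the calls.**
- Day 3: 72 − 48 = 24 h to 72 − 36 = 36 h after the second call.
- Day 5: 120 − 48 = 72 h to 120 − 36 = 84 h after the second call.

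For a patient first examined on day 3 or day 5, both calls are over before the examination. No complication question is required before about 72 h or 120 h.

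**Step 4. Why the early period counts.** The Background says that most corneal abrasions heal on their own within 48 hours. Both calls lie inside that period, and a first examination on day 3 or day 5 lies after it. A complaint that comes and goes in the first two days may therefore be over by the time of the required assessment.

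**Step 5. What the other required items cover.** A problem that raises pain would show in the pain score at a call. One that causes little pain need not. Because the lens is meant to relieve pain (Aims I and II), pain may also be a weaker warning sign in the lens arm. That is an inference, not a statement in the protocol.

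**Step 6. Can the effect be sized?** That would need the rate of complaints that appear and resolve before the visit and go unmentioned there, and the share of patients asked in each arm. The protocol gives none of these, so no estimate is offered. The hours in Step 3 describe the schedule; they do not measure bias.

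**The case against.** The best defence is that the main safety source is already mandatory and sound. An ophthalmology examination is a better detector of lens complications than a telephone question. The appointment is due in both arms, and the Exclusion Criteria remove patients thought unlikely to attend. On this view the calls are a supplement and the text contains no contradiction. This largely stands. It confines the gap to early or transient problems and to patients who miss the visit.

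It can also be said that question lists usually sit in a call script or case report form. The protocol refers to attached participant contact materials that are not shown. Whether they include a script is unknown, so the ambiguity at the calls is something the text permits, not an established failure. If a fixed script exists, the protocol only needs to be brought into line with it.

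Two stronger readings are tempting, and the documents support neither.

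- **Biased complication counts.** A reader might infer that lens patients will be asked more often than usual-care patients, creating a false excess of complications in the lens arm. The first call is stated for both groups and the optional sentence draws no distinction between arms. Differential asking is possible but nowhere indicated. Any calculation that counts a complaint only if it is raised by telephone also ignores the required visit.
- **Uninterpretable wear time.** A reader might infer that lens complications cannot be read because wear at the examination runs from about 24 to 120 hours. That range describes a lens still in place at a first visit. Several visits are allowed, and actual wear can be shorter or longer. Reporting by wear time is largely a matter for the analysis plan, and making the call questions mandatory would not change the range.

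**Conclusion.** The point holds as a cheap improvement to safety ascertainment. Complication questions are neither required nor standardised at the two calls, and the only required safety data come from a visit that may first occur on day 3 or day 5. Early problems that resolve before that visit can be recorded unevenly between patients or arms.

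The size cannot be determined from the protocol, and the visit, the required pain scores and the return instructions all limit it. The conclusion rests on the protocol text alone: it assumes that no call script outside the document already fixes the questions, and that callers may know the treatment. It does not affect the pain comparison, and it does not show that recorded complications will be biased.

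**What to change.** In Study Design and Methods, replace the optional sentence after each of the two calls with: *A fixed set of complication questions, identical in both groups, will be asked.* Add that a positive answer prompts the return to the ED or ophthalmology clinic for which the discharge instructions already provide. Optionally, record the date and reason for lens removal, so that complications can be read alongside wear time if the analysis plan calls for it. The ophthalmology schedule stays as it is.

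The cost is two reworded sentences, a short question list for calls already scheduled and, if wanted, two data fields. The downside is slightly longer calls, possibly a few unscheduled rechecks, and probably more minor complaints recorded in both arms. In return, an answer of no complication at a completed call has the same meaning for every patient.

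### Safety examinations can differ in number and timing between the arms, because only lens patients must be examined until healed and no common safety period is set

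*Protocol*

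**What the plan says.** All of the follow-up text is in the Protocol, Study Design and Methods.

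- **Lens arm:** "The contact lens will be removed when the examining follow-up provider has deemed that the abrasion has healed". The patient is told this in the ED and in written instructions, and the follow-up provider is told by letter.
- **Usual care:** "UC subjects will have usual care provided in the ED per the ED consultant". No healing-based end to examination is given.
- **Visits, no arm named:** "A follow-up appointment with Ophthalmology will occur at 1 day, 3 days, and/or 5 days post-discharge, depending on specific patient factors, patient needs, clinic availability". The visit is described as standard of care: "any patient presenting to the ED with a corneal abrasion will be scheduled for a follow-up visit with Ophthalmology".
- **Return instructions, given before patients leave:** "All patients will be given follow-up instructions regarding when to return to the ED, ophthalmology clinic, etc. for BCL removal and recheck prior to ED" (the quote stops one word short of the end of the sentence).
- **Telephone calls:** the first is "between 12-24 hours after ED treatment to assess their pain scores" and the second is at 36-48 hours. Both are timed from ED treatment, and questions on complications are optional at each.
- **Source of safety data:** "Data will be obtained from the follow-up ophthalmology visit regarding safety, adverse events and any complication of the lens wear". No common time window is stated.

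Aim III (Research Question and Aims) asks whether the lens is safe and practical, and names no comparator. The comparison comes from the Data Analysis section, which plans to weigh the advantages and disadvantages of the lens against usual care.

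**The concern.** A complication is recorded only if someone looks for it. The one stated rule that forces a further examination applies to one randomised arm. How many visits a usual-care patient has is left to patient factors, patient needs and clinic availability. The opportunity to find a complication can therefore depend on assignment and on healing, which the assignment may itself affect.

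Planned contact also stops early. The second call, at 36-48 hours, comes before any day 3 or day 5 visit. A complication that arises after such a visit, in either arm, has no planned route into the data.

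At stake is the safety half of the comparison with usual care. A difference in complication counts could reflect how often patients were examined and not what the lens does. An absence of difference could hide events that came later.

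**Working it through.** The protocol gives no complication rate, attendance or detection figure, so there is no stated result to reproduce. The target accrual of 200 comes without statistical inputs, and this point does not depend on it. The two calculations below show only how large the effect could be. Both assume that the true risk is the same in the two arms.

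**1. Unequal number of examinations**

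Share of complications detected = attendance × (1 − (1 − d)^v), where d is detection per examination and v is the number of examinations. All values of attendance, d and v are assumptions.

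| Usual care | Lens | Ratio, lens to usual care |
|---|---|---|
| 0.75 × 0.60 = 0.450 (one visit, d = 0.6) | 0.95 × (1 − 0.4²) = 0.95 × 0.84 = 0.798 (two visits) | 0.798 / 0.450 = 1.77 |
| 0.90 × 0.60 = 0.540 (one visit, d = 0.6) | 0.798 (two visits) | 0.798 / 0.540 = 1.48 |
| 0.80 × 0.70 = 0.560 (one visit, d = 0.7) | 0.95 × (1 − 0.3²) = 0.95 × 0.91 = 0.8645 (two visits) | 0.8645 / 0.560 = 1.54 |
| 0.95 × 0.60 = 0.570 (one visit, d = 0.6) | 0.95 × 0.60 = 0.570 (one visit) | 1.00 |

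With a true risk of 5%, the first row gives 0.05 × 0.450 = 2.3% against 0.05 × 0.798 = 4.0%. At an assumed 100 patients per arm that is about 2 against 4 patients. The first three rows all assume more visits for lens patients. The last row shows that the effect disappears when both arms are seen alike.

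**2. Unequal time to the last examination**

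Detected risk = 1 − exp(−h × t). Here h is an assumed constant daily hazard, equal in both arms, and t is the day of the last examination, taken from the protocol's own days 1, 3 and 5.

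| Last examination, lens v usual care | h = 1% | h = 2% | h = 5% | Ratio |
|---|---|---|---|---|
| day 5 v day 3 | 4.9% v 3.0% | 9.5% v 5.8% | 22.1% v 13.9% | 1.65 to 1.59 |
| day 5 v day 1 | 4.9% v 1.0% | 9.5% v 2.0% | 22.1% v 4.9% | 4.90 to 4.54 |
| day 1 v day 3 | 1.0% v 3.0% | 2.0% v 5.8% | 4.9% v 13.9% | 0.34 to 0.35 |
| day 5 v day 5 | 4.9% v 4.9% | 9.5% v 9.5% | 22.1% v 22.1% | 1.00 |

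The second row is an extreme. It supposes that every patient in an arm has the same last day, and that nothing is learned from the telephone calls or from unplanned care. The third row shows the direction reversing if lens patients heal, have the lens out and stop attending sooner. The last row is what a common period gives: a ratio of 1.0 at every hazard.

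**The case against.** Several parts of the text work against a large effect.

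- Every patient is scheduled for an ophthalmology visit, the day 1, 3 and/or 5 schedule is not split by arm, and all patients receive recheck instructions. Subject Information excludes patients judged unlikely to attend ophthalmology. A reader might infer that usual-care patients go largely unexamined, and the protocol does not support that. What stands is that a shared initial appointment does not equalise later ones. The patient instructions are attachments not shown here, so a recheck rule for usual care may exist there.
- A reader might also infer that observation of lens patients ends when the lens comes out. The protocol says no such thing. It sets no end of observation in either arm, and the 36-48 hour call falls due even after a day 1 removal. What stands is narrower: no contact is planned after a day 3 or day 5 visit, in either arm.
- Most abrasions are said to heal within 48 hours, so a single day 3 visit might both confirm healing and remove the lens. In that case the arms could be examined equally often.
- Aim III has no comparator, and some of the safety data concern lens wear, which cannot arise in usual care. A descriptive account of safety in the lens arm stays readable. Only the comparison is affected.
- An analysis plan that is not shown could define a safety window. It could not supply records or answers that nobody planned to collect.

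**Conclusion.** The point holds as a risk that the wording permits, not as a bias that it prescribes. Examination until healing is required in the lens arm only, visits are otherwise open, safety data come from those visits, and no common period is set. The number and timing of safety examinations can therefore differ by arm, and complications after a day 3 or day 5 visit fall outside planned data collection.

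The documents determine neither the direction nor the size. The ratio is 1.0 if both arms are seen alike. It is about 1.5 to 1.8 under the assumed attendance and detection figures, all of which favour more examination of lens patients. It falls below 1 if lens patients are followed for less time. It would be too strong to say that the lens count is inflated, or that the safety comparison cannot be read at all. It may be biased either way, and it can be made firmer cheaply before data are collected.

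**What to change.** In Study Design and Methods:

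1. Define the safety comparison as any eye complication or unplanned eye care within one fixed period from randomisation. The period should be identical in both arms, independent of lens removal, and longer than the last scheduled visit. Thirty days is only an example; the documents give no basis for a particular length.
2. Count each patient once, by medical-record review. The identifier table under HIPAA Identifiers and Protected Health Information already lists "Mayo Clinic medical record or patient registration number" and dates.
3. Make the complication questions compulsory, and the same for both arms, at both telephone calls.
4. Count complications found at lens-removal visits in the comparison. Leaving them out would hide lens complications.
5. Report the number of eye examinations per patient by arm. Consider a sensitivity comparison limited to complications that led to treatment or unplanned care, since these depend less on how often a patient is examined.

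The cost is one record review per patient and a few scripted questions; no visits are added. Two limits remain. Care received elsewhere may be missed, and record review does not fully equalise how intensively the arms are examined. The clinical rule for lens removal is not changed.
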